8.0 SELECTION AND WITHDRAWAL OF PATIENTS

Subjects will be selected on the basis of the following inclusion and exclusion criteria.

8.1 Inclusion Criteria

Subjects will be eligible if they meet all of the following criteria:

1. Willing and able to provide informed consent for the trial, written, electronic, verbal, or other method deemed acceptable by the institution and IRB.
2. Subjects between ≥ 18 and ≤ 65 years of age.
3. Subjects found positive for SARS-CoV-2 either by rapid antigen test or by reverse transcription polymerase chain reaction (RT-PCR) using ICMR-validated kit.

Note: Test need not be repeated in those with possession of confirmed positive report but positive result test date must be ≤ 5 days of first dose of study drug.

4. Mild or Moderate COVID-19 as per latest updated version of CLINICAL MANAGEMENT PROTOCOL for COVID-19 (in Adults) released by Government of India Ministry of Health and Family Welfare Directorate General of Health Services (EMR Division).
5. The effects of brequinar on the developing human fetus are unknown. For this reason, women of child-bearing potential and men must agree to use adequate contraception (hormonal or barrier method of birth control; abstinence) prior to study entry and for the duration of study participation. Should a woman become pregnant or suspect she is pregnant while she or her partner is participating in this study, she should inform her treating physician immediately. Men and women treated or enrolled on this protocol must also agree to use adequate contraception for the duration of study participation, and for 90 days after completion of brequinar administration.
6. Male subjects must agree to refrain from sperm donation and female subjects must agree to refrain from ovum donation from initial study drug administration until 90 days after the last dose of brequinar.
7. At least one non-respiratory COVID-19 symptom characterized as moderate to severe by the Investigator including but not limited to fatigue, chills, fever, body aches, nasal congestion, nausea, vomiting, or other sign or symptom commonly associated with COVID-19 in the opinion of the investigator. Symptom onset must be ≤ 5 days prior to first dose. Subject must have one or more signs/symptoms present at first dose.
8. Willing to participate in the PK subset if at one of the identified sites.
9. Able to swallow capsules.

Protocol for clinical study of Brequinar
 Protocol No.: 21-VIN-0372
 Version No.: 2.1; Dated: 29 Dec 2021
 Supersedes: 02; Date of Supersedes: 30 Sep 2021

8.2 Exclusion Criteria

Subjects will not be eligible for this study if any of the following in present at the time of study inclusion:

1. Have an oxygen saturation of <90% while breathing ambient air.
2. Any physical examination findings and/or history of any illness that, in the opinion of the study investigator, might confound the results of the study or pose an additional risk to the subject.
3. Nursing women or women of childbearing potential (WOCBP) with a positive pregnancy test.
4. Treatment with another DHODH inhibitor (e.g., leflunomide, teriflunomide) or other agents known to cause bone marrow suppression leading to thrombocytopenia.
5. Ongoing treatment with aspirin and or dipyridamole, famotidine or cimetidine. Remdesivir and ivermectin are prohibited through Study Day 8. Steroids are permitted per the guidelines.
6. Platelets \leq 125,000 cell/mm³.
7. Hemoglobin <10 gm/dL.
8. Absolute neutrophil count <1000 cells/mm³.
9. Renal dysfunction, i.e., creatinine clearance <30 mL/min.
10. AST or ALT $>$ 3 x ULN, or total bilirubin $>$ ULN. Gilbert's Syndrome is allowed.
11. Bleeding disorders or blood loss requiring transfusion in the six weeks preceding enrollment.
12. Ongoing gastrointestinal ulcer, or gastrointestinal bleeding within 6 weeks of first dose.
13. HIV, Chronic hepatitis B infection, active hepatitis C infection, active liver disease and/or cirrhosis per subject report.
14. Heart failure, current uncontrolled cardiovascular disease, including unstable angina, uncontrolled arrhythmias, major adverse cardiac event within 6 months (e.g., stroke, myocardial infarction, hospitalization due to heart failure, or revascularization procedure).

8.3 Withdrawal Criteria

Subjects may voluntarily withdraw from the study at any time without assigning any reason thereof by withdrawing their consent. They may be considered withdrawn if they state an intention to withdraw, or fail to return for visits, or become lost to follow up for any other reason.

If premature withdrawal occurs for any reason, the investigator must determine the primary reason for a patient's premature withdrawal from the study and record this information in the CRF. For patients who are lost to follow-up (i.e., those patients whose status is unclear because they fail to appear for study visits without stating an intention to withdraw), the investigator should show "due diligence" by documenting in the source documents steps taken to contact the patient, e.g., dates of telephone calls, other means of communication even though patient is unwilling to attend further visits etc.

If study participation is discontinued, the final evaluation will be performed as completely as possible. Any comments (spontaneous or elicited) or complaints made by the patient and the reason for termination, date of stopping the study medication and the total amount of study medication must be recorded in the source documents or CRFs.

Protocol for clinical study of Brequinar

Protocol No.: 21-VIN-0372

Version No.: 2.1; Dated: 29 Dec 2021

Supersedes: 02; Date of Supersedes: 30 Sep 2021

Criteria for a withdrawal of patients from clinical study:

The subject may be withdrawn from the trial at the discretion of the investigator or the sponsor, if judged non-compliant with trial procedures or due to safety concern.

A subject must in addition be withdrawn from treatment with IMP if the following applies:

- AE requiring permanent discontinuation of study drug.
- The subject suffers from significant intercurrent illness or undergoes surgery requiring study discontinuation during the course of the study.
- Any subject who requires the use of an unacceptable concomitant medicine.
- If the Investigator believes it is not in the subject's best interest to continue.
- The subject wishes to withdraw his/her consent.
- Any other justifiable reason, which should be adequately documented.
- Any subject whose condition worsens, requiring treatment with immunomodulators including but not limited to tocilizumab and / or antiviral drugs including but not limited to remdesivir as per the best judgement of the Investigator.
- Non-compliance: The participant may be withdrawn from the trial at the discretion of the Investigator if it is judged that participant is non-compliant to study assessment and schedule leading to safety concerns.
- Positive pregnancy test: A female participant with a positive pregnancy test will be withdrawn from the trial.

The sponsor or its representative may be contacted for clarification as required on a case-by case basis.

Handling of Withdrawals:

In the case of premature discontinuation of study subject, the investigator should schedule a study discontinuation visit to complete all assessment according to End of Study / Early Termination visit requirements. All reasons for ending participation must be recorded in the source documents or in the CRF.

If the subject discontinues because of an adverse event (serious or non-serious), the investigator must follow up patient's recovery until resolution or stabilization of AEs or up to 30 days after administration of last dose of IMP, whichever is earlier.

This visit should be documented in the appropriate section of the Case Report Form (CRF). The investigator will record the reason for study discontinuation, provide or arrange for appropriate follow-up for such subjects, and document the course of the subject's condition. In addition, the investigator will report the subject's withdrawal to the responsible study monitor immediately.

Subjects withdrawn from investigational product treatment will be treated as routine subjects. The investigator will discuss the appropriate therapy with each subject who withdraws early from this study. Determination of the appropriate follow-on therapy will be left to the discretion of the investigator and investigator could treat such subjects as per his/her routine practice.

Protocol for clinical study of Brequinar
 Protocol No.: 21-VIN-0372
 Version No.: 2.1; Dated: 29 Dec 2021
 Supersedes: 02; Date of Supersedes: 30 Sep 2021

9.0 STUDY PROCEDURE

9.1 Study Design

The first part of the study will be a phase II, randomized, assessor-blind, multicenter, multi-dose, placebo-controlled study in approximately 64 subjects with mild to moderate COVID-19 infection confirmed by a positive SARS-CoV-2 RT-PCR qualitative test /rapid antigen test and who have at least mild to moderate signs and/or symptoms ongoing at study entry.

Approximately 32 subjects (50% of subjects per arm per cohort) at selected sites will be invited to participate in the “PK” arm of the study until approximately 8 subjects in each cohort have been recruited after providing written informed consent for the same. PK includes brequinar and dipyridamole plasma concentrations.

If a particular cohort meets study stopping criteria (as defined in section “Stopping Criteria”) or is found to be unsafe by DSMB members, then the study will not proceed with enrollment of subsequent cohorts.

An expansion cohort of approximately 48 subjects will be added to the cohort with the highest brequinar dose that meets safety criteria.

Safety data of cohort 1 to cohort 4 (or highest dose cohort evaluated) will be submitted to the regulators and their approval will be obtained prior to commencing recruitment in the expansion cohort.

All subjects will receive SOC as per relevant guidelines for treatment of patients with mild to moderate COVID-19 infection.

Subjects will be randomized to one of the following cohorts in Part 1:

Cohort 1:

- Arm 1: 5 days of standard of care (SOC) + brequinar 50 mg OD + dipyridamole 75 mg TID (N = 8)
- Arm 2: 5 days of SOC + brequinar 50 mg OD (N = 4).
- Arm 3: 5 days of SOC + brequinar placebo 50 mg OD (N = 4).

Cohort 2:

If the 50 mg brequinar OD + dipyridamole 75 mg TID meets safety criteria as pre-defined in the protocol the brequinar dose will be escalated to 100 mg.

- Arm 1: 5 days of standard of care (SOC) + brequinar 100 mg OD + dipyridamole 75 mg TID (N = 8)
- Arm 2: 5 days of SOC + brequinar 100 mg OD (N = 4).
- Arm 3: 5 days of SOC + brequinar placebo 100 mg OD (N = 4).

Cohort 3:

If the 100 mg brequinar OD + dipyridamole 75 mg TID meets safety criteria as pre-defined in the protocol the brequinar dose will be escalated to 150 mg:

Protocol for clinical study of Brequinar

Protocol No.: 21-VIN-0372

Version No.: 2.1; Dated: 29 Dec 2021

Supersedes: 02; Date of Supersedes: 30 Sep 2021

- Arm 1: 5 days of standard of care (SOC) + brequinar 150 mg (100 mg + 50 mg) OD + dipyridamole 75 mg TID (N = 8)
- Arm 2: 5 days of SOC + brequinar 150 mg (100 mg + 50 mg) OD (N = 4)
- Arm 3: 5 days of SOC + brequinar placebo 150 mg (100 mg + 50 mg) OD (N = 4).

Cohort 4:

If the 150 mg brequinar OD + dipyridamole 75 mg TID meets safety criteria as pre-defined in the protocol the brequinar dose will be escalated to 200 mg:

- Arm 1: 5 days of standard of care (SOC) + brequinar 200 mg (100 mg +100 mg) OD + dipyridamole 75 mg TID (N = 8)
- Arm 2: 5 days of SOC + brequinar 200 mg (100 mg +100 mg) OD (N = 4)
- Arm 3: 5 days of SOC + brequinar placebo (100 mg + 100 mg) OD (N = 4).

Expansion Cohort:

Approximately forty-eight (48) subjects will be added to the cohort with the highest brequinar dose that meets safety criteria in a 2 : 1 ratio of active treatment (approximately 32 in SOC + brequinar + dipyridamole treated and 16 in SOC + brequinar monotherapy group). Additional sites may be added if required to meet enrollment of the expansion cohort in an efficient manner.

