7.0 STUDY ENDPOINTS

Primary Endpoints:

- Frequencies of grade 3 and 4 toxicities and serious adverse events (SAEs) considered by the investigator to be related to the combination, brequinar alone or placebo alone.

Secondary Endpoints:

- qPCR SARS-CoV-2 levels through Day 29 and at days 4, 8, 12, 15, 22, and 29;
- Time to symptom improvement through Day 29;
- Percentage of subjects requiring hospital admission/re-admission as an in-patient for >24 hours through Day 29;
- Percentage of subjects requiring medical attended visits, e.g., hospitalization, emergency room visits, Urgent Care/Family Doctor visits through Day 29;
- Percentage of subjects requiring supplemental support such as oxygen through Day 29.

Exploratory Endpoints (PK):

- Analysis of brequinar's pharmacokinetic profile in a subset of patients that have received brequinar as a part of therapy and have consented to provide PK samples.

Clinical improvement will be defined as a 2-point or greater improvement on an 8-point WHO ordinal scale in every subject measured on each designated day, from the date of randomization through day 29. This scale has been used in the current COVID-19 outbreak.

Ordinal Scale for Clinical Improvement

Patient State	Descriptor	Score
Uninfected	No clinical or virological evidence of infection	0
Ambulatory	No limitation of activities	1
	Limitation of activities	2
Hospitalized	Hospitalized, no oxygen therapy	3

Protocol for clinical study of Brequinar

Protocol No.: 21-VIN-0372

Version No.: 2.1; Dated: 29 Dec 2021

Supersedes: 02; Date of Supersedes: 30 Sep 2021

Mild disease	Oxygen by mask or nasal prongs	4
Hospitalized	Non-invasive ventilation or high-flow oxygen	5
Severe Disease	Intubation and mechanical ventilation	6
	Ventilation + additional organ support – pressors, RRT, ECMO	7
Dead	Death	8

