9.6 Sample Size

No statistical powering has been performed for this study. The number of subjects is designed to provide information on the safety, tolerability, and efficacy of the IMP tested in this study. In Part 1, approximately 64 subjects will be randomized to up to 4 cohorts of 5 consecutive days of one of the following regimens in addition to SOC in 2:1:1 ratio as shown below:

Treatment Arm ^a	Day 1	Day 2	Day 3	Day 4	Day 5
Brequinar + Dipyridamole (N=8)	BRQ XX mg OD DPY 75 mg TID				
Brequinar (N=4)	BRQ XX mg OD				
Placebo (N=4)	PBO XX mg OD				

Protocol for clinical study of Brequinar

Protocol No.: 21-VIN-0372

Version No.: 2.1; Dated: 29 Dec 2021

Supersedes: 02; Date of Supersedes: 30 Sep 2021

^aAll subjects will also received standard of care (SOC).

The brequinar dose will start at 50 mg and may be escalated to 100 mg, 150 mg, and 200 mg if safety criteria are met for each cohort (see Safety Criteria below).

The hospital pharmacist is to be unblinded. Bulk supplies of investigational medicinal product (IMP) of brequinar 50 mg, brequinar 100 mg, dipyridamole 75 mg, brequinar placebo 50 mg and brequinar placebo 100 mg will be supplied to the unblinded hospital pharmacist.

The unblinded hospital pharmacist is to prepare the assigned IMP for each individual subject at that institution and create an appropriately labeled bottle/zip lock bag of study medication sufficient for a 5-day treatment course. The randomization assignment will be provided via an IWRS.

Alternatively, the hospital pharmacist and study team may decide to distribute IMP on a daily basis for 5 days for brequinar and dipyridamole while the subject is hospitalized, depending on the most convenient method.

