12.9 Handling and Reporting of Adverse Events

An adverse event is any untoward medical occurrence (including a symptom or disease or an abnormal laboratory finding) during treatment with an investigational drug or a pharmaceutical product in a subject that does not necessarily have a relationship with the treatment being given.

*Abnormalities based on laboratory parameters, vital signs, and 12-Lead ECG will be called AE, if they are associated with at least one of the following:

- Interruption or stoppage of the study medication
- Associated with signs or symptoms
- Requiring treatment
- Considered clinically significant by the investigator

Safety Criteria:

An independent, unblinded study physician (from CRO) will assess each cohort for safety. A cohort will be declared safe as soon as all results are available for the Day 15 visit if the following conditions are met:

- No toxic deaths (deaths judged by the investigator to be related to either study drug);
- Not more than 1 toxic SAE (SAEs judged by the investigator to be related to either study drug);
- No Grade 3 or higher toxicities (including laboratory AEs as per CTCAE version 5.0 or higher) (AEs judged by the investigator to be related to either study drug);
- <4 subjects with any grade toxicity (AEs judged by the investigator to be related to either study drug).

In addition to the cohort-level safety, the independent study physician (from CRO) will determine if any subjects meet Individual Stopping Criteria:

- Subjects who develop a Grade 3 toxicity that is assessed by the investigator to be related to the study drug are to be permanently discontinued from study treatment but will continue in the study for safety assessments.
- Subjects who develop a Grade 4 toxicity, regardless of relatedness to study drug, are to be permanently discontinued from study treatment but will continue in the study for safety assessments.

In addition to the individual subject-level safety, the independent study physician (from CRO) will determine if a cohort meets Cohort-level Stopping Criteria prior to completing the 16 subjects, in which case no additional subjects will be enrolled into that cohort and no higher brequinar doses will be assessed:

Protocol for clinical study of Brequinar

Protocol No.: 21-VIN-0372

Version No.: 2.1; Dated: 29 Dec 2021

Supersedes: 02; Date of Supersedes: 30 Sep 2021

- ≥ 3 brequinar-treated or combination-treated subjects meet the individual stopping criteria.

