15.5 Safety Analysis

All safety analysis will be conducted using the safety population set.

Frequency distribution or summary statistics of all demographics variable and baseline characteristics will be generated by treatment arm.

The evaluation of the drug safety will be based on clinical AEs, vital signs, physical examination, concomitant medications and laboratory abnormalities reported during the study and incidence of adverse events and treatment emergent adverse events in each arm during the study. All safety presentations will include subjects who receive at least one dose of the study medication and will group subjects by treatment received. Frequency distributions and individual listings of all adverse events will be generated. Changes in clinical laboratory test results from baseline will be listed.

A treatment emergent adverse event is defined as any event not present prior to the initiation of the treatments or any event already present that worsens in either intensity or frequency following exposure to the treatments.

Adverse events will be coded using Medical Dictionary for Regulatory Activities (MedDRA) terms using the version that is current at the time the first subjects is enrolled and will be summarized by system organ class (SOC) and preferred term within SOC. The Common Terminology Criteria for Adverse Events CTCAE 5.0 will be used to grade the severity of adverse events.

Protocol for clinical study of Brequinar

Protocol No.: 21-VIN-0372

Version No.: 2.1; Dated: 29 Dec 2021

Supersedes: 02; Date of Supersedes: 30 Sep 2021

Adverse Events will be summarized by treatment and overall. AE summary tables will include counts of subjects and the number of events. If a subject experiences more than one episode of a particular AE, that subject will be counted only once for that event. If a subject has more than one AE that coded to the same preferred term, the subject will be counted only once for that preferred term. Similarly, if a subject has more than one AE within a SOC, the subject will be counted only once in that SOC.

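### If the expansion is combined with the Part 1 cohort that earned it, the related Grade 3+ rate at the selected dose is understated by up to 20% relative; the plan should show the two separately

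*Combined protocol and SAP*

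**What the plan says.** Section 9.6 describes Part 1: about 64 "subjects will be randomized to up to 4 cohorts", with arms in a 2:1:1 ratio. The combination arm is "Brequinar + Dipyridamole (N=8") per cohort, and brequinar alone and placebo have 4 each. Section 9.1 then states "An expansion cohort of approximately 48 subjects will be added to the cohort with the highest brequinar dose that meets safety criteria" and splits the addition as "approximately 32 in SOC + brequinar + dipyridamole treated and 16 in SOC + brequinar monotherapy group".

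The Safety Criteria in Section 12.9 decide which cohort qualifies. They are applied once Day 15 results are available and require "No Grade 3 or higher toxicities (including laboratory AEs as per CTCAE version 5.0 or higher"), counting events the investigator judges related to either study drug. They also allow "Not more than 1 toxic SAE (SAEs judged by the investigator to be related to either study drug"), rule out toxic deaths and cap the number of subjects with any related event at fewer than 4.

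Section 7.0 defines the primary endpoint as the frequencies of Grade 3 and 4 toxicities and SAEs "considered by the investigator to be related to the combination, brequinar alone or placebo alone". Section 15.3 has one safety population: everyone randomized who takes at least one dose. On presentation, Section 15.5 says "Adverse Events will be summarized by treatment and overall"; the synopsis says results are shown by group, without defining group. Section 15.4 plans no formal test of the primary endpoint, and Section 15.1 leaves further detail to a separate SAP whose text is not in the document reviewed here.

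**The concern.** The variable that selects the dose is also the main part of the primary endpoint. A cohort that passed has no related Grade 3+ event through Day 15 because a cohort with one would not have passed. Its subjects therefore cannot give an unselected estimate of that rate. The expansion subjects can, because they are enrolled after the choice is made.

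The endpoint is descriptive, so the reported rate and any interval around it are the primary result. Section 5.5 says that the combination has not been tested in the clinic before. A combined figure would make the selected dose look somewhat safer than it is, in a known direction, and nothing in Section 15 tells the reader of the table that part of the denominator was selected on the outcome.

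**Working it through.** **Inputs.** Part 1, per cohort: 8 combination, 4 brequinar alone, 4 placebo (Section 9.6). Expansion: about 32 combination and 16 brequinar alone (Section 9.1). Gate: zero related Grade 3+ events on Day 15 results (Section 12.9). The plan states no toxicity rate, so p, the true related Grade 3+ rate at the selected dose, is an assumed range up to 20%.

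**The plan's own figures.** 4 × (8 + 4 + 4) = 64, and 32 + 16 = 48 at 2:1. Both reproduce.

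**Expected pooled rate.** Suppose first that all events arise by Day 15. The selected cohort contributes zero events and the expansion contributes its expectation:

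- combination: (0 + 32p)/(8 + 32) = 0.8p
- brequinar alone: (0 + 16p)/(4 + 16) = 0.8p

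The understatement is 20% relative in both arms. For the combination, against the ordinary standard error √(p(1−p)/40):

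| True p | Pooled mean | Bias (points) | SE, n = 40 (points) |
|---|---|---|---|
| 2% | 1.6% | 0.4 | 2.2 |
| 5% | 4.0% | 1.0 | 3.4 |
| 10% | 8.0% | 2.0 | 4.7 |
| 20% | 16.0% | 4.0 | 6.3 |

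**Events after Day 15.** The gate does not see these. If a share f of events first arises after Day 15, a subject in a cohort that passed still has probability fp/(1 − (1−f)p) of an event. At p = 10% and f = 25% this is 0.025/0.925 = 2.7%, so the pooled mean is (3.2 + 8 × 0.027)/40 = 8.54%, which is 14.6% below the truth. At f = 10% and 50% the understatement is 17.8% and 9.5%.

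**No events observed.** The exact two-sided 95% upper limit is 1 − 0.025^(1/n). This gives 10.9% for 0/32 and 8.8% for 0/40. For brequinar alone it gives 20.6% for 0/16 and 16.8% for 0/20.

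**Interval coverage at the selected dose.** With X ~ Binomial(32, p) and Clopper-Pearson limits computed as X/40, coverage is 99.6%, 99.5%, 96.2%, 96.2% and 96.6% at p = 2%, 5%, 10%, 15% and 20%. Between those rates it can dip below nominal. At p = 17%, for instance, the upper limit for 2/40 is 16.9%, so 0, 1 or 2 events miss the truth (probability 7.3%); with 0.1% missed on the other side, coverage is 92.6%. At p = 10% the upper limit falls below the truth 3.4% of the time, against 1.5% for 40 unselected subjects.

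**Bias against precision.** At p = 10% the root mean squared error of the pooled figure is √(2.0² + 4.24²) = 4.7 points, where 4.24 = 100 × √(32 × 0.09)/40. For the expansion alone it is 100 × √(0.09/32) = 5.3 points.

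**The case against.** The strongest reply is that the plan never says the two groups are pooled. Adding subjects to a cohort describes enrolment and dose, one safety population does not fix table columns, and the SAP with its mock tables may separate them. This stands: pooling is what the wording suggests, but it is not prescribed. The separation is not prescribed either, and that is the gap.

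The second reply is that the effect is small. The bias is under one standard error across the assumed range, there is no test or decision threshold on the pooled rate, and the pooled estimate has the smaller mean squared error. Section 9.1 also has Part 1 safety data go to regulators before the expansion. This stands too, and it is why the expansion need not be the only figure reported.

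A reader might infer three stronger things that the documents do not support:

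- **That the whole primary endpoint is understated by construction.** One related SAE is tolerated at the gate, so a related SAE below Grade 3 can remain in the selected cohort, and events after Day 15 are not conditioned on.
- **That the interval at the selected dose fails badly.** The coverage above stays close to nominal.
- **That an all-dose combination rate would be halved.** That needs four doses merged into one rate and all four cohorts to pass. With 12 brequinar-treated subjects per cohort and the same p at each dose, the chance of this on the Grade 3+ rule alone is (1−p)^48, or 0.64% at p = 10%. If a failing cohort is included, an all-dose rate is understated by about 8% to 16% for p from 1% to 20%, given that an expansion takes place. Over all possible trial outcomes it is overstated (by 24% at p = 10%), because some trials stop early on an event with few subjects.

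**Conclusion.** The concern holds in a limited form. The selection rule is in the text. The combining of Part 1 with the expansion is implied but not stated. If they are combined, the related Grade 3+ rate at the selected dose is understated by up to 20% relative in both arms (2 points at a true 10%), and with no events the combination upper limit reads 8.8% in place of 10.9%.

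The figures assume independent subjects, a constant rate within a dose and no related event on placebo. The full 20% also needs every event to arise by Day 15. This is a modest bias of known direction in a descriptive primary endpoint. It calls for clearer reporting and does not undermine the design.

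**What to change.** In Section 15.5 and the SAP, tabulate the primary endpoint by dose, with the expansion (about 32 combination and 16 brequinar alone) and the Part 1 cohorts in separate columns, each with an exact 95% confidence interval. Any figure that pools Part 1 with the expansion may stay, labelled as conditional on the cohort having passed the safety criteria. The synopsis should define group to match.

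The cost is one extra table split and a wider interval for the unselected estimate. No data are dropped, and the design, doses and safety criteria are untouched.
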